6.3.3 Prohibited concomitant therapy

The following medications are prohibited during the study:

- Any investigational medication (other than PANOBINOSTAT) that is not approved for any indication. Use of such medications within 30 days, prior to the first dose of study drug and during the study through the Safety Follow-up Visit is prohibited.
- Use of strong inducers of CYP3A4 (e.g. avasimibe, carbamazepine, phenobarbital, phenytoin, rifabutin, rifampin, St. John's wort) is not permitted at any time during the study. (See Appendix 1 for further details)
- Patients who are currently receiving treatment with any of the medications which have a relative risk of prolonging the QT interval or inducing Torsades de Pointes and cannot either discontinue this treatment or switch to a different medication prior to study enrollment, will be excluded from the study. Patients may not begin treatment with any of the medications while receiving study treatment unless approval is given by the Investigators to temporarily discontinue study treatment during administration with these drugs. Should a patient already enrolled on this study require short-term (i.e. approximately \leq 2 weeks) treatment with these drugs, study treatment must be interrupted for at least 72 hours prior to starting these drugs and should not resume until at least 72 hours after the last dose of such a drug or longer (i.e. 5 half-lives) as listed.
- Any use of drugs that interferes with coagulation or inhibits platelet function (including non-steroidal anti-inflammatory drugs), with the exception of:
 - Aspirin \leq 81 mg/day
 - LMWH, direct thrombin inhibitors, anti-10a inhibitors as long as INR remains less than 1.5
- Any other medication for the treatment of myelofibrosis, including but not limited to:
 - Hydroxyurea
 - Busulfan
 - Interferon
 - Lenalidomide

- Thalidomide
- Anagrelide
- Any hematopoietic growth factor receptor agonists (including but not limited to: erythropoietin, romiplostim, or eltrombopag). The use of G-CSF can be used as discussed in Section 6.3.2.

6.3.4 Dose reduction of RUXOLITINIB for concomitant strong CYP3A inhibitor usage

RUXOLITINIB is metabolized in the liver by the cytochrome (CYP) P450 metabolizing enzyme system, predominantly by the 3A4 isozyme. With concomitant dosing of strong CYP3A4 inhibitors such as systemic ketoconazole, clarithromycin, itraconazole, nefazodone and telithromycin (Appendix 1), plasma exposure of RUXOLITINIB increases approximately 2-fold. Patients under therapy with a strong CYP3A4 inhibitor cannot be enrolled in the study. Use of strong CYP3A4 inhibitors during Cycle 1 of the study is prohibited. Use of strong CYP3A4 inhibitors after Cycle 1 Day 28 is strongly discouraged, and investigators should consider alternative therapies wherever possible. However, if the use of a strong CYP3A4 inhibitor is necessary for the sake of patient's safety, then a dose reduction of ~ 50% for RUXOLITINIB is mandatory. The following dose-reduction rules must be followed:

- If dose is 5 mg bid., change dose to 5 mg qday
- If dose is 10 mg bid., change dose to 10 mg qday
- If dose is 15 mg bid., change dose to 15 mg qday

NOTE: once the course of therapy using a CYP3A4 inhibitor has been completed, the patient may resume his/her prior dose level of RUXOLITINIB beginning the next day.

6.4 Patient numbering, treatment assignment and randomization

6.4.1 Patient numbering

Each patient is uniquely identified in the study by a unique patient number (001, 002, etc), that is assigned when the patient is first enrolled for screening and is retained as the primary identifier for the patient throughout his/her entire participation in the trial. Upon signing the informed consent form, the patient is assigned to the next available sequential patient number. Once a number is assigned, it cannot be reused for any other patient and the patient number for that individual must not be changed, even if the patient is re-screened.

If patient signed informed consent but fails to start the study treatment, the reason will be entered into the Screening Log eCRF page.

6.4.2 Treatment assignment and randomization

The assignment of a patient to a particular cohort will be coordinated by the investigator.

6.4.3 Treatment blinding and Randomization

Not applicable

6.5 Study drug supply

6.5.1 Study drug preparation and dispensation

Both RUXOLITINIB and PANOBINOSTAT capsules including instructions for administration, will be dispensed by site study personnel on an outpatient basis. Patients will be provided with adequate supply of study drug for self-administration at home until at least their next scheduled study visit.

6.5.2 Study drug packaging and labeling

The investigators at MSSM will be supplied with oral PANOBINOSTAT and oral RUXOLITINIB by Novartis. The packaging will contain a 2-part label. Immediately before dispensing study drug to the patient, authorized clinical site staff member will detach the outer part of the label from the packaging and affix it to the source document (Drug Label Form) containing the patient's unique patient number. Medication labels will comply with the legal requirements of the United States. The storage conditions for study drug will be described on the medication label.

As with all anti-cancer drugs, their preparation and administration should be closely supervised by a qualified physician (Study Investigator) experienced in the use of cancer chemotherapeutic agents.

RUXOLITINIB

RUXOLITINIB tablets will be provided in bottles. Medication labels will be in the local language and comply with the legal requirements of each country. They will also include storage conditions for the drug.

PANOBINOSTAT

Oral PANOBINOSTAT will be supplied as 5-mg, 10-mg (when available), or 20-mg hard gelatin capsules and will be given on a flat scale of mg on a given day. The capsules are packaged in HDPE bottles with plastic child resistant closures.

Store in very tight packaging (water permeation <0.5ng/day/L) at 15°C to 30°C (room temperature) and protect from light.

6.5.3 Drug supply and storage

Study treatments must be received by a designated person at the study site, handled and stored safely and properly, and kept in a secured location to which only the investigator and designated assistants have access. Upon receipt, the study treatment should be stored according to the instructions specified on the drug labels.

6.5.4 Study drug compliance and accountability

6.5.4.1 Study drug compliance

Dosing frequency and compliance will be assessed by the investigator and/or study personnel at each patient visit and information provided by the patient and/or caregiver will be captured in the Drug Accountability Form. This information must be captured in the source document at each patient visit.

6.5.4.2 Study drug accountability

The investigator or designee must maintain an accurate record of the shipment and dispensing of study treatment in a drug accountability ledger. Drug accountability will be noted by the field monitor during site visits and at the completion of the study. Patients will be asked to return all unused study treatment and packaging on a regular basis, at the end of the study or at the time of study treatment discontinuation.

At study close-out, and, as appropriate during the course of the study, the investigator will return all used and unused study treatment, packaging, drug labels, and a copy of the completed drug accountability ledger to the the Pharmacy at MSSM.

6.5.5 Disposal and destruction

The drug supply can be destroyed at the local Novartis facility, Drug Supply group or third party, as appropriate.

7 Visit schedule and assessments

7.1 Visit schedule

Appendix 2 lists all of the assessments and indicates with an “X”, the visits when they are performed. All data obtained from these assessments must be supported in the patient’s source documentation and data will be captured in the e-CRF.

7.1.1 Pre-screening assessments

Not applicable

7.1.2 Screening

Below is a brief description of the screening tests/procedures for this protocol. The screening window is 56 days. The informed consent must be signed prior to any screening procedure. For details of assessments, refer to Appendix 2.

- Inclusion/Exclusion
- Demographics
- Relevant medical history / Current Medical Conditions
- Myelofibrosis (MF) disease history
- Diagnosis of PMF, PPV MF and PET-MF
- Prior and current concomitant medications and Significant non-drug therapies
- Transfusion history
- Physical Examination
- Vital signs, Weight and Height
- ECOG
- 12-Lead ECG
- ECHO or MUGA
- Chest X Ray PA/Lat
- Biomarkers (blood for genomic, epigenomic and cellular studies)
- Buccal swab
- Cytokine profile
- Measurement of spleen by palpation in craniocaudal length
- MRI/CT of spleen
- Laboratory Safety Tests including the following: Hematology, Biochemistry, Coagulation, Thyroid, Urinalysis and serum Pregnancy, quantitative JAK2V617F and/or MPL, cytogenetics
- Bone Marrow biopsy/aspirate (should be done at screening but if a specimen is available within 3 months of screening and the patient has not had any MF-directed therapy during this period, a biopsy during the screening period can be omitted)
- MPN-SAF

7.1.2.1 Eligibility screening

Patients must meet all inclusion and exclusion criteria at Screening in order to be eligible for the study. Patient eligibility will be confirmed by the investigative staff and captured within the source documents maintained at the site. Only when eligibility is confirmed will the patient be assigned to a dose level. The Primary Investigator/co-investigators must approve eligibility and will assign the patient to the appropriate dose level.

7.1.2.2 Information to be collected on screening failures

Patients who sign an informed consent but fail to be started on treatment for any reason will be considered a screen failure. The reason for not being started on treatment will be entered on the Screening Log. The demographic information must also be completed for Screen Failure patients. No other data will be entered into the clinical database for patients who are screen failures. If a patient experiences a Serious Adverse Event during the Screening Phase it will be captured in the source documents and eCRF but the patient will not be considered as evaluable within the dose cohort level and this data will not contribute to dose escalation decisions.

7.1.2.3 Patient demographics and other baseline characteristics

At the screening visit, the following data should be collected/evaluated and recorded on the appropriate eCRF:

- Complete demographic information (age, gender, race, body weight, and height)
- Complete medical (including MF) history
- Medication history (prior and concomitant, including those used to treat MF)
- Prior JAK2V617F mutational status (if available before the signature of the Informed Consent Form) or any other MPN molecular marker
- Review of Packed Red Blood Cells (PRBC) transfusion history (for the last 12 weeks prior to Screening).
- Adverse Events
- Eastern Cooperative Oncology Group (ECOG) status
- Pregnancy test performed and prevention methods will be discussed
- Spleen length below the left costal margin by palpation
- Vital signs (blood pressure, pulse, respiratory rate and body temperature)
- 12-lead electrocardiogram (ECG)
- Complete physical examination
- Buccal swab for germline DNA banking
- Clinical laboratory tests (Biochemistry panel, hematology, and coagulation tests, urinalysis, TSH and fT4)
- Cytokine profile sample
- Chest X ray
- MPN-SAF

All medications and significant non-drug therapies (e.g. herbs) taken within 14 days before the first dose is administered must be recorded updated on a continual basis if there are any new changes to the medications. Medications include physician prescribed and over-the-counter medications, as well as vitamins and herbal and alternative therapies. Information to be collected on concomitant medications/significant non-drug therapies will include the following:

- Medication/Non-drug therapy trade name

- Reason for medication
- Start date and end date or continuing at time of exam

In addition to the general demographic and relevant medical history information, study specific information will be collected during the screening period as indicated in the assessment schedule (Appendix 2) in order to determine eligibility of the patient.

7.1.3 Run-in period

Not applicable

7.1.4 Treatment period

7.1.4.1 Cycles 1-6 [core study period]

Patients may continue study treatment through the first 6 cycles, unless they progress, withdraw consent, experience intolerable toxicity, start new MF therapy, and/or based on investigator discretion, it is believed to be in the best interest of the patient to discontinue. Cycle 1 will be the dose evaluation period for those patients enrolled in the phase I portion of the study and can continue on to complete the 6 cycles of therapy if they did not experience a DLT.

7.1.4.2 Cycle 7+ (Day 169+) [extension phase]

Following the completion of the first 6 cycles, the patient may continue study onto if they are continuing to receive clinical benefit and the investigator believes it is in the best interest of the patient. After 24 cycles, stable patients may be seen every other month at the discretion of the investigator. Assessment by IWG-MRT response criteria will be applied to determine the patient has achieved at least Stable Disease (SD) and therefore is eligible for continued therapy. Refer to Table 4-1.

7.1.5 End of treatment visit, including premature withdrawal and study discontinuation visit

Patients who discontinue study treatment should be scheduled for an end of treatment visit, at least 30 days post-last dose of treatment. 30 day post last dose, end of study visit will include: history, physical exam, Hematology, Biochemistry, and ECG. An End of Treatment Phase Disposition eCRF page should be completed, giving the date and reason for stopping the study treatment. At a minimum, all patients who discontinue study treatment, including those who refuse to return for a final visit, will be contacted for safety evaluations during the 30 days following the last dose of study treatment.

For criteria for premature withdrawal refer to Section 7.1.5.1.

7.1.5.1 Criteria for premature patient withdrawal

Patients may voluntarily withdraw from the study or be removed at the discretion of the investigator at any time. If such withdrawal occurs, or if the patient fails to return for visits, the investigator must determine the primary reason for a patient's premature withdrawal from

the study and record this information on the appropriate eCRF. Patients may be withdrawn from the study prematurely for one of the following reasons:

- Adverse event(s)
- Abnormal laboratory value(s)
- Abnormal test procedure result(s)
- Protocol deviation
- Subject withdrew consent
- Lost to follow-up
- Administrative problems
- Death
- Initiation of new cancer therapy
- Disease progression
- The investigator determines that further therapy is not in the patient's best interest (e.g., due to non-compliance, toxicity etc.).

Patients who experience disease progression, start of new anti-cancer therapy, or withdraw consent, must be permanently discontinued from the study.

For patients who are lost to follow-up, the investigator should show "due diligence" by documenting in the source documents steps taken to contact the patient, e.g., dates of telephone calls, registered letters, etc.

Patients must be followed for 30-days post-last treatment of study drug.

7.1.5.2 Replacement policy

Patients prematurely withdrawn from the study will not be replaced, however in the phase I portion of this study, from Cycle 1 Day 1 through Day 28, a patient misses more than 11 oral administrations of RUXOLITINIB or more than 1 dose of PANOBINOSTAT in QOW dosing or 2 doses in the QW dosing, the patient can continue in the study without being evaluable for DLTs. Consequently an additional patient may be added to the same dose level in order to reach the required number of patients in the cohort. See Section 10.4.3 for specific details.

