6.2.3 Criteria for dose escalation and determination of MTD and/or RPTD

A patient will be considered evaluable for the dose-determining set if he or she experiences a DLT during the combination phase days 1 to 28, or is observed for at least 28 days in the combination phase and is fully evaluated for any toxicities and has completed all study required tests. Patients who do not experience a DLT in the 28 days of the combination phase are considered evaluable if they have taken at least 50% of the RUXOLITINIB doses and not missed more than 1 dose of PANOBINOSTAT in the QOW dosing cohorts and no more than 2 doses in the QW dosing cohorts.

All available safety information (including DLTs, adverse events that are not DLTs, vital signs, and ECGs will be reviewed by the investigators in each cohort to decide if the next dose cohort will begin. Drug administration at the next dose level may not proceed until the investigators have documented it is safe to proceed to a higher dose level. Dose escalation will continue until identification of the MTD and/or RPTD is made.

The initial 3 cohorts will have RUXOLITINIB administered at a fixed dose of 10mg PO BID and cohort 1 will combine PANOBINOSTAT at a dose of 10mg PO TIW QOW, cohort 2 will be PANOBINOSTAT 15mg PO TIW QOW and cohort 3 will be PANOBINOSTAT 20mg PO TIW QOW for cumulative cycle doses of 60mg, 90mg and 120mg, respectively. If an MTD of PANOBINOSTAT is not established by cohort 3, then cohort 4a will test RUXOLITINIB at 15mg PO BID in combination with PANOBINOSTAT 15mg PO TIW QOW and 20mg PO TIW QOW in 4b. If an MTD of PANOBINOSTAT is established in the first 3 cohorts, then the cohort 4a will test RUXOLITINIB at 15mg PO BID in combination with PANOBINOSTAT at the dose level preceding the MTD dose level of PANOBINOSTAT.

If the dose escalation of RUXOLITINIB continues to cohort 4b and this cohort does not define the MTD of RUXOLITINIB, then cohort 5 will allow patients to be treated at a dose of PANOBINOSTAT of 10mg PO TIW QW for a cumulative dose/cycle of 120mg. Cohorts 6 and 7 will be pursued if the previous cohorts don't reach MTD and will include 15mg PO BID of RUXOLITINIB and 15mg PO TIW QW and 20mg PO TIW QW, respectively.

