6.2.4 Dose cohort modification

Provisional dose level cohorts are listed in Table 6-2. Possible changes in dose administration include but are not limited to:

- Expansion of the current dose group to further assess safety
- Administration of an intermediate dose between the current and preceding dose
- Administration of an intermediate dose between the current and the next planned dose
- Termination of any further escalation of study drug

If there is less than the required number of evaluable patients, then additional patients will be enrolled until at least the minimum number of evaluable patients is available for assessment.

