6.2.6 Follow-up for toxicities

Patients whose treatment is interrupted or permanently discontinued due to an adverse event or abnormal laboratory value must be followed at least once a week for 4 weeks up to day 28. Patients whose treatment is interrupted or permanently discontinued due to an SAE, must be followed at least once a week for 4 weeks up to day 28, and subsequently at 4-week intervals, until resolution or stabilization of the event, whichever comes first. If a patient requires a dose delay for either drug for longer than 90 days from the intended day of the next scheduled dose, then the patient must be discontinued from the study. Hematology labs (CBC) and pertinent non-hematology labs will be part of the follow up procedures. ECG will also be part of the follow up procedures if the AE/SAE was cardiac related.

All patients will be followed for AE's and SAE's for 30 days following the last dose of study treatment, with the exception of prolonged QTc.

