10.1.4 Dose-determining set

The dose escalation analysis and the determination of the MTD and/or RPTD will be based on the set of evaluable patients in every dose cohort where evaluability is defined in Section 6.2.3.

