10.4.3 Handling of missing values/censoring/discontinuations

During the dose-finding part of the trial, one additional patient may be enrolled in each cohort, for each patient who does not meet the criteria necessary for inclusion in the dose-determining set. During the dose expansion part of the trial, one additional patient may be enrolled for each patient who does not meet the criteria necessary for inclusion in the safety set. At the time of the writing of the study report, patients will have continuing events (e.g., adverse events) summarized using the data cut-off date as the date of completion, with an indication within the listings that the event is continuing.

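### The Cycle 1 evaluability limits conflict and ignore why doses were missed, so a patient stopped by related toxicity short of a DLT can fall outside the 3+3 count

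*Combined protocol and SAP*

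**What the plan says.** **Who is evaluable.** Under Section 6.2.3, a patient with a DLT in Days 1-28 is evaluable whatever the dose count. A patient without one must be observed for 28 days, fully evaluated and have all required tests. Such patients "are considered evaluable if they have taken at least 50% of the RUXOLITINIB doses and not missed more than 1 dose of PANOBINOSTAT" for the every-other-week (QOW) cohorts, or 2 doses for the weekly (QW) cohorts.

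**Who may be replaced.** Section 7.1.5.2 keeps the same panobinostat limits but sets another ruxolitinib limit. If a Phase I patient "misses more than 11 oral administrations of RUXOLITINIB" in Days 1-28, "the patient can continue in the study without being evaluable for DLTs", and a further patient may join the cohort. The same section says that withdrawn patients are not replaced. Section 6.2.4 says that if a cohort is short, "then additional patients will be enrolled until at least the minimum number of evaluable patients is available for assessment". Section 10.4.3 says that "one additional patient may be enrolled in each cohort, for each patient who does not meet the criteria necessary" for the dose-determining set.

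**What the set decides.** Under Section 10.1.4, the escalation analysis and the MTD and/or RPTD "will be based on the set of evaluable patients in every dose cohort", with evaluability taken from 6.2.3.

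**What counts as an event.** Section 6.2.5 confines DLTs to Table 6-3, and Section 4.1 adds a platelet transfusion judged necessary. Neither covers failure to complete Cycle 1 because of related toxicity.

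**How doses can be lost.** Section 6.2.7 bars interruptions for related events in Phase I Cycle 1, then speaks of removing a patient with a DLT. Section 7.1.5.1 allows withdrawal when further therapy is not in the patient's "best interest (e.g., due to non-compliance, toxicity etc". Section 6.2.6 sets follow-up to Day 28 for a pause or stop in treatment: those "permanently discontinued due to an adverse event or abnormal laboratory value must be followed at least once a week for 4 weeks".

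**The concern.** There are two faults. First, the sections disagree on who is in the set that determines the MTD, so the same DLT-free patient can be counted or dropped depending on which section is applied. Second, no section separates a patient who missed doses for an unrelated reason from one who could not tolerate them. Replacing the first is ordinary 3+3 practice. Replacing the second removes a patient whose missing doses are themselves evidence about tolerability.

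Safety and tolerability are part of the Phase I primary objective (Section 10.4). Up to 30 Phase I patients (42 less the 12 enrolled through cohort 3, Section 10.8) remain to be assessed in cohorts 4a to 7, at the higher ruxolitinib dose and, from cohort 5, on weekly panobinostat. Thirty is an enrollment ceiling and not a count of patients affected.

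**Working it through.** **1. The two ruxolitinib limits.** Twice daily for 28 days gives 2 x 28 = 56 doses. Section 6.2.3 needs at least 28 taken, so up to 28 may be missed. Section 7.1.5.2 makes a patient non-evaluable from 12 missed. They conflict for 12 to 28 missed, with panobinostat within limits.

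**2. When an early stop fails the dose count.** Using the example days in Section 6.1.1, panobinostat QOW falls on Days 1, 3, 5, 15, 17 and 19 (6 doses; 60 mg / 10 mg in Table 6-2). QW gives 12 doses (120 mg / 10 mg). If both drugs stop after day d, ruxolitinib missed = 2 x (28 - d).

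| Schedule | Last day | Panobinostat missed | Ruxolitinib missed | 6.2.3 dose count | 7.1.5.2 |
|---|---|---|---|---|---|
| QOW | 16 | 2 of 6 | 24 | fails | fails |
| QOW | 17 | 1 of 6 | 22 | meets | fails |
| QOW | 22 | 0 of 6 | 12 | meets | fails |
| QW | 21 | 3 of 12 | 14 | fails | fails |
| QW | 22 | 2 of 12 | 12 | meets | fails |
| Either | 23 | 0 (QOW), 2 (QW) | 10 | meets | meets |

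A patient withdrawn for toxicity is still followed to Day 28, so a later DLT would be looked for. Without one, the patient can fail on doses alone. Whether or not a replacement is enrolled, a patient who fails is not counted.

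**3. Effect on the 3+3 decision.** This applies the rules of Section 10.4.2.1, assuming that such patients are replaced, that replacements are DLT-free and that the investigators follow the count.

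| Cohort | True position | Replaced | Counted as a DLT |
|---|---|---|---|
| First 3 | 1 such patient, no DLT | 0/3, escalate | 1/3, expand |
| First 3 | 2 such patients, no DLT | 0/3, escalate | 2/3, MTD exceeded |
| First 3 | 1 such patient, 1 DLT | 1/3, expand | 2/3, MTD exceeded |
| 6 | 1 such patient, 1 DLT | 1/6, escalate | 2/6, MTD exceeded |

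**4. Illustration with assumed rates.** P(escalate) = (1-p)^3 + 3p(1-p)^5. At p = .05, .10, .20, .30, .40, .50 and .60 this gives .973, .906, .709, .494, .309, .172 and .082, which matches the lower row of the table in Section 10.8 (.97, .91, .71, .49, .31, .17, .08).

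The documents give no rate for toxicity-driven misses, so take an assumed rate q with a true DLT rate of 20%. Replacement makes the rule see 0.20/(1-q); counting makes it see 0.20 + q.

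| q | Combined rate | P(escalate), replaced | P(escalate), counted |
|---|---|---|---|
| 5% | 25% | .686 | .600 |
| 10% | 30% | .660 | .494 |
| 15% | 35% | .632 | .396 |
| 20% | 40% | .600 | .309 |

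Keeping such patients as DLT-free would give .709, so replacement is already the stricter of the two non-counting options. The calculation ignores the investigator review.

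**The case against.** The strongest reply is that the plan already deals with most of this. Most grade 3-4 non-hematologic toxicity is a DLT, and so is a needed platelet transfusion. Section 6.2.3 forbids escalation until the investigators document that it is safe. Section 6.2.5 feeds non-DLT events into escalation and all events into the final MTD/RPTD analysis. Section 6.2.4 allows expansion, intermediate doses or stopping. The 6.2.7 sentence might be meant to make any needed related interruption a DLT. All of this stands as mitigation, but the review is judgment outside the counting rule, and neither 6.2.7 nor Table 6-3 actually says that such an interruption is a DLT.

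Three stronger readings are not supported:

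- A reader might infer that DLTs are being hidden. They are not: a DLT in Days 1-28 makes a patient evaluable regardless of doses.
- A reader might infer that patients with platelets of 10 to <20 x10^9/L without a grade 3 bleed or needed transfusion, or with afebrile ANC <0.5 x10^9/L, drop out of the count. Managed per protocol, they keep dosing in Cycle 1 and are counted as DLT-free. The interruptions in Table 6.2.3 start on Day 29 in Phase I. The DLT thresholds are a deliberate choice (Sections 4.1 and 6.2.5) and not part of this gap.
- A reader might infer that the plan escalates past the 33% limit of Section 6.2.3.1. That limit applies to dose-limiting toxicity, so adding misses to it presumes the redefinition. Even then, at a 20% DLT rate, misses would have to exceed 33 - 20 = 13 percentage points, and no document gives a rate.

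**Conclusion.** The point holds in a limited form. The conflict between 6.2.3 and 7.1.5.2 is an error on the face of the text and affects any DLT-free patient missing 12 to 28 of 56 ruxolitinib doses with panobinostat within limits. Section 10.1.4 points to 6.2.3 for the dose-determining set, but that does not remove the contrary instruction in 7.1.5.2.

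The failure to ask for a reason is a real gap reached by narrow routes: doses the patient skips, a hold made despite the 6.2.7 ban, or discretionary withdrawal. Its frequency is unknown. Its size is best stated per patient: one or two can change a cohort decision if the investigators follow the count. The escalation probabilities rest on assumed miss rates and are illustrative only. It should be corrected before further cohorts open.

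**What to change.** 1. Use one ruxolitinib limit in Sections 6.2.3 and 7.1.5.2, for example no more than 11 of 56 missed, so that a patient counted as DLT-free has had adequate exposure.
2. In Sections 6.2.3, 7.1.5.2 and 10.4.3, allow replacement only when doses were missed, or the patient left in Days 1-28, for reasons unrelated to study drug. A patient who exceeds the limit or is withdrawn in Days 1-28 because of a new or worsened treatment-related event of grade 2 or higher, documented as preventing dosing, stays in the dose-determining set, counts as a DLT and is not replaced. Say the same in Section 6.2.7 and Table 6-3.
3. Apply this to cohorts opened after the amendment. If an earlier cohort is reopened for de-escalation, as Section 10.8 foresees for cohort 3, assess all its patients under one definition from existing records.

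**Cost.** This is a short amendment, but it changes the DLT definition during escalation and needs IRB approval. The data are already collected: action taken for each adverse event (8.1.1), withdrawal reason (7.1.5.1) and dosing compliance (6.5.4.1). Escalation may stop a level earlier, sometimes at a dose within the 33% limit; in the illustration, a 30% combined rate takes P(escalate) from .660 to .494. Some expected cytopenias would count when they cost enough doses. With an 11-dose limit, a six-day ruxolitinib hold for grade 4 neutropenia misses 6 x 2 = 12 doses and would be a DLT, although Table 6.2.3 restarts later-cycle patients at an unchanged dose if it resolves within 7 days. The investigators should accept that consequence knowingly or set the limit differently.
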